**13. Please describe the research design and all study related procedures.**

- *Describe **ALL PROCEDURES ASSOCIATED WITH THIS RESEARCH**. This includes standard of care and research procedures.*
- *For complex studies please include diagrams and tables. Be sure to describe when each procedure will be performed. Be sure to provide information for **each cohort, including normal controls**).*

Patients cohorts (n=30).

Enrollment. [name] will be responsible for enrolling all patients for the study, whether he is the primary neurologist caring for the patients or whether they are being referred to him for possible enrollment in the study.

All patients will undergo neurological evaluation (medical history, clinical neurological examination, including eye movements exam, and blood work for renal function panel) prior to selection to establish whether or not they meet the study inclusion criteria. Possible female participants will also undergo a urine pregnancy test. [name] will evaluate all patients as above.

Randomization and masking. Patients will be randomized to study drug or placebo for the first 4 weeks of treatment then, after a wash-out period of at least 2 weeks, they will cross-over to placebo and study drug respectively for another 4 weeks of treatment. Randomization process will be carried out by a VA research pharmacist. The patient, the PI, and all personnel and investigators involved in the study will be masked to treatment assignment. To avoid the possibility of a patient running out of the study drug/placebo at the time of the

2nd or 4th visit, for example in case of visit cancellation due to unforeseeable circumstances, the study drug/placebo will be sent out for 5 weeks. However, every effort will be made to schedule patients as close as possible to the 4-week mark for the 2nd and 4th visit. Additionally, all unused study medications will be returned by the subject to the laboratory at the 2nd and 4th visits.

Procedures to be performed at Evaluation 1 ,2 ,3 ,4.

Video tape of subjects' eye movements.

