**Eye Movement Recording.** Eye movements will be recorded using the EyeLink II system, (SR Research Ltd.). Subjects will sit in a 110-ft-lb vestibular chair (CNC Engineering), with head restrained, during all the experimental paradigms, and will follow a visual stimulus (a red laser spot) projected onto tangent screen. The EyeLink signal from each eye will be calibrated. We will obtain a baseline monocular and binocular viewing recording of eye movements then will perform the 10-minute saccadic fatigue test as previously described [Matta et al, 2009]. Patients will make horizontal saccades in response to 20-degree jumps, at 0.5 Hz across the midline (i.e., 1 saccade per second), of the visual target (laser spot).

At evaluations 2 and 4, patients will hold the am dose (dalfampridine or placebo), will undergo baseline eye movement recording, then will be recorded again 3 hours after taking their dose in the same session.

Visual function assessment using MNREAD acuity charts for reading acuity and speed and the King-Devick test for saccades performance. [name] will carry out these assessments.

Symptomatic fatigue assessment using self-administered questionnaires: the Fatigue Severity Scale (FSS) and the Modified Fatigue Impact Scale (MFIS).

Gait assessment using the 25-foot Walk Test and the 6-minute Walk Test. [name] will carry out these assessments.

Visual disability and quality of life assessment using the following self-administered scales: NEI-VFQ-25 and NOS; and the MS Quality of Life Inventory.

Renal function panel (serum) at baseline, to be repeated after 4 weeks and at the end of the trial. Phlebotomy will be performed by a lab technician in the blood work laboratory located in the first floor of the LSDVAMC.

Normal controls cohort (n=20).

**Enrollment.** [name] will be responsible for enrolling all age-matched normal controls for the study, including possibly residents, house staff and employees of the LSDVAMC and Case.

All controls will undergo clinical evaluation of vision and eye movements to confirm they have normal visual and ocular motor functions.

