**40. Describe all procedures that minimize risks, please include study and standard of care procedures:**

We will not enroll subjects in which AMYRA is contraindicated: history of seizure, moderate or severe renal impairment, history of hypersensitivity to AMPYRA or similar compounds. To minimize possible side effects, subjects will be taking the FDA-recommended dose of AMPYRA (10 mg tablet twice daily), with doses taken approximately 12 hours apart and only taken whole. Subjects will be advised not to take double or extra doses if a dose is missed.

Since AMPYRA can cause side effects, especially seizures, in subjects with abnormal renal function, this will be checked through standard blood work at baseline, after 4 weeks and at the end of the study.

We will keep all eye movement recordings under 30 minutes to minimize possible discomfort.

If subjects do not wish to answer a question in a questionnaire, they may skip it and go to the next question.

To ensure confidentiality of patient's records, we will keep all records on a password-protected computer in Room BC 300c in the Daroff-Dell'Osso Ocular Motility Laboratory. This computer has an encryption firewall. Paper records will also be kept in a locked cabinet in Room BC 300c; the keys to the room and cabinet will be retained by [name]. Each patient will be assigned a number based on the hour and date of their study. The key to the numbers/patients will be stored in [name] password-protected computer and in the memories of each patient and [name]. At the end of the study, all data will be stored on a password-protected CD, kept in [name] locked cabinet and will be retained indefinitely.

**41. Describe alternative procedures or course of treatment, if any, which might be advantageous to the subject. State if no alternatives exist or if this is not a treatment study.**

AMPYRA is potentially available to subjects outside of the research study with the FDA-approved indication for gait impairment. Because of the nature of this research the only alternative is to not participate in this study. Currently, there are no other approved treatment/drugs for the treatment of INO.

**Minimal Risk:** Minimal risk means that the risks of harm anticipated in the proposed research are not greater, considering probability and magnitude, than those ordinarily encountered in daily life or during the performance of routine physical or psychological examinations or tests.

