**51. Please describe how informed consent will be obtained from subjects who do not read or understand English;**

- *identify any languages likely to be encountered, and attach a copy of a translated and authenticated informed consent document*
- *It is appropriate to indicate that you do not anticipate encountering potential subjects who do not speak English based on the population to be studied*

We will not recruit subjects who do not speak English.

**52. Describe who (by Role ex. PI, Coordinator, etc.) and how it will be determined that subjects and/or legally authorized representative understand the research and their rights.**

- *ex. question and answer, repeat back parts of the research, describe a procedure...etc*

By engaging the patient in an unhurried conversation, with ample time for them to ask questions and discuss the nature of the study described by the PI. In order to maintain the blinding of the study, subjects will be advised that the pill of AMPYRA they will be taking in the study may or may not look like the AMPYRA that is commercially available and that they may have taken in the past. Also, the subjects will be advised not to discuss the pill they are taking, its appearance, possible side effects they may be experiencing, with [name] or other people conducting the eye movement recording and the other assessments of this study. If experiencing any side effect or if they have questions about the pill they are taking, subjects can contact [name] (contact info can be found in the consent form).

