**71. Drug Information for each drug listed in the protocol -check as applicable**

Approved Drugs

Not Approved

- Attach VA Form 10-9012 Investigational Drug Information Record for each drug used in the protocol
- Attach Package Insert or PDR monograph – copy ready, 8.5 x 11 for each drug listed in the protocol
- Attach Investigator's Brochure

**72. Provide a detailed description of how FDA-regulated drugs/biologics will be stored, secured, dispensed, administered, tracked, and returned.**

The Cleveland VA Research Pharmacy procures the study medication. It then stores, dispenses and tracks the study medication. If any study medication is returned to the PI, then he returns it to the Cleveland VA Research Pharmacy.

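### Unused tablets are returned to the laboratory at both on-treatment visits, which gives masked assessors an avoidable chance to see them, and no readable section says that drug and placebo look alike

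*Combined protocol and SAP*

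**What the plan says.** **Who is masked.** Section 3, item 13 (randomization and masking): "The patient, the PI, and all personnel and investigators involved in the study will be masked to treatment assignment".

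**How appearance is treated.** Section 6, item 52 sets out a blinding safeguard: "subjects will be advised not to discuss the pill they are taking, its appearance, possible side effects they may be experiencing". The people they must not tell are those doing the eye movement recordings and the other assessments. The same item warns patients that the study pill might or might not resemble the marketed product.

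**Where leftover tablets go.** Item 13: "the study drug/placebo will be sent out for 5 weeks", as a reserve against a delayed visit, although visits are to be kept close to four weeks. At the 2nd and 4th visits "all unused study medications will be returned by the subject to the laboratory". Section 9, item 72 adds: "If any study medication is returned to the PI, then he returns it to the Cleveland VA Research Pharmacy".

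**In-session dose.** At Evaluations 2 and 4 the morning dose is held and a baseline recording made. Patients "then will be recorded again 3 hours after taking their dose in the same session" (item 13). Item 12 ticks drug administration for clinical or support staff and not for research staff. It ticks clinical tests and eye movement recording for research staff.

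**The concern.** The plan itself treats tablet appearance as something assessors should not learn. It closes the verbal route and leaves a physical one open: patients may not describe the tablet, but they bring it to the laboratory at the two visits where on-treatment outcomes are measured.

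The crossover design raises the stakes, because each patient brings tablets from both periods to the same team. If drug and placebo differed visibly and one were recognised, both periods would be known for that patient, and possibly for later patients. Prior users of dalfampridine are eligible (item 30), so the marketed tablet may be familiar to some participants.

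At stake are outcomes that a study team member carries out with the patient: MNREAD, King-Devick, the 25-foot walk and the 6-minute walk. An assessor who knows or suspects the period can influence how such tests are conducted, most plausibly in favour of the drug.

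**Working it through.** The plan states no figure on this point, so there is none to reproduce. The check sets the provisions side by side and counts the tablets.

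**1. Does the return route meet the masked team?** Item 13 names only the laboratory. Item 8 names the ocular motility laboratory as the place where the study is conducted, and item 48 has patients come there to be studied. A blood work laboratory is also mentioned in item 13, but the ocular motility laboratory is the natural reading. Item 72 separately allows returns to reach the PI, whom item 13 masks. No readable section says that returns are sealed, that an unmasked person receives them, or that they are handed over only after the assessments.

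**2. Are returns routine?** Inputs: 5 weeks supplied and a visit near week 4 (item 13); one tablet twice daily (item 40), used here only to size the returns.

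- Supplied per period: 5 × 7 × 2 = 70 tablets.
- Taken by week 4 with full adherence: 4 × 7 × 2 = 56 tablets.
- Left over: 70 − 56 = 14 tablets, give or take the in-session dose.
- If the visit slips to the end of week 5: 70 − 70 = 0 tablets.
- Planned returns: 30 patients × 2 visits = up to 60.

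Returns with tablets in them are therefore the expected case, not the exception. These figures count handovers. They do not measure unmasking or bias.

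**3. Which outcomes are exposed?** Item 10 lists ten numbered measures, two in each of five groups. Item 13 has a member of the study team carry out the visual function and gait groups, so 2 + 2 = 4 of the 10 are run by an assessor. The fatigue, visual disability and quality-of-life measures are self-administered. The two conjugacy measures are peak-velocity and peak-acceleration quantities from the eye tracker.

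**4. What is said about matching?** Item 52 compares the study pill with the commercial one. No readable section compares drug with placebo. Two cases follow:

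- *Tablets indistinguishable:* seeing them reveals nothing, and the harm is nil.
- *Tablets distinguishable:* assessors can be unmasked through returns. Patients, who take both products, can be unmasked too, whatever the return route.

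**5. Is the in-session dose a second exposure?** Item 13 places it in the same session, without naming the room or who is present. Item 12's allocation of drug administration to clinical or support staff could keep it away from assessors, but no procedure links the two items. This is the weaker half of the point.

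**The case against.** The strongest reply is that nothing in the documents suggests the tablets differ. The trial is described throughout as double-blind and placebo-controlled. Masking a patient who takes each product for four weeks is hard without matching tablets. Product details may also sit in attachments that item 71 calls for, or in pages not available for review. This stands, and it limits the point to a safeguard left incomplete plus one missing statement on matching.

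A second reply is that sealing the returns misses the root cause: if the tablets did differ, patients would be unmasked as well, and the self-reported scales and effort on the walk tests would be affected. That is also right, and it is why the fix includes the statement on appearance.

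Four stronger readings are tempting and are not supported:

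- *That a site following the plan necessarily shows assessors both tablets.* Item 13 does not say that an assessor receives, opens or counts the returns. A closed bottle passed on to the pharmacy would comply.
- *That the held dose is swallowed in front of assessors.* Item 13 names neither place nor witness, and item 12 points the other way.
- *That the eye movement measures are biased through marking of saccades by hand, or the walk tests through encouragement.* The documents describe neither practice. The pulse measures behind the first two sample-size calculations in item 11 are instrument-derived and less open to assessor influence.
- *That up to 60 returns gives the scale of bias.* It gives only the number of handovers.

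These replies do not remove the mismatch between item 52, which keeps appearance from assessors, and items 13 and 72, which bring the tablets to the laboratory and possibly to the PI.

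**Conclusion.** The point holds as a cheap improvement to the masking procedures, not as a demonstrated failure of the blind. As written, the return route works against the plan's own safeguard and can let assessors see a patient's tablets from both periods. The opportunity is routine for patients seen on schedule (about 14 tablets per visit with full adherence) and nearly vanishes for a visit at the end of week 5. Four of the ten listed measures are the most exposed.

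The size of any bias cannot be estimated from the documents. It is zero if drug and placebo are indistinguishable. The conclusion rests on two assumptions: that the laboratory receiving returns is the one where outcomes are assessed, and that matching is not settled in material unavailable here. No sample size, power or analysis figure is affected.

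**What to change.** 1. **Returns.** Amend items 13 and 72 so that unused tablets come back in a sealed opaque container, go to the Research Pharmacy unopened by anyone who assesses outcomes, and are counted there if a count is wanted. The pharmacy already tracks the product and is where item 72 says returns end up.
2. **Appearance.** Confirm in the protocol that drug and placebo are identical in appearance. If that cannot be confirmed, patient masking needs its own solution, because sealed containers do not address it.
3. **In-session dose (secondary).** Reconcile items 12 and 13 by stating that the dose at Evaluations 2 and 4 is handled by the clinical or support staff already assigned, away from outcome assessors. Nothing about the dose or its timing changes.

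**Cost:** a few sentences of protocol text, opaque pouches, and the loss of any same-day tablet count in the laboratory, which the documents do not require. No new staff role is needed if the item 12 allocation is followed, though someone from that group must be available at those two visits.

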needed to generate a saccade along the demyelinated MLF, which might be representative of a major component of primary motor fatigue in MS. The second part of the project concerns testing the effects of dalfampridine (a potassium channel blocker that enhances neural conduction along demyelinated axons) on MS-related INO with or without associated ocular motor fatigue. Visual dysfunction in MS patients with INO is a major cause of disability but no medical therapy is available. Our preliminary results document improved binocular conjugacy in three MS patients taking dalfampridine. In this respect, our hypotheses are: 1) dalfampridine improves visual performance in MS patients with INO and counteracts ocular motor fatigue; 2) improvement of INO and ocular motor fatigue with dalfampridine diminishes visual disability and improves quality of life in MS.

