**10. Describe the means of analyzing the data and evaluating the results.**

- *State the anticipated methods to be used for analysis and interpretation of the data.*
- *The methods must compliment the design of the study and the nature of the data which is being collected.*

This study investigates horizontal binocular conjugacy and ocular motor fatigue in MS patients with INO and the effects of treatment (dalfampridine) while eye movements are recorded during a 10-minute saccadic fatigue test. Patients will undergo clinical eye movement examination, visual performance assessment including reading acuity and speed, gait assessment, assessment of symptomatic fatigue, disability arising from visual dysfunction as well as quality of life, using available self-administered questionnaires and scales, and eye movement recording, before and after treatment. The treatment portion of the study will be conducted following a randomized, placebo-controlled, double-blind, crossover trial design, which will include a period of wash out of at least two weeks between treatment with dalfampridine and placebo. A minimum of 2 weeks is necessary to ensure wash out, however a washout period longer than 2 weeks will not confound the study results. There will be a total of 4 evaluations: at baseline, after washout, and after treatment with both dalfampridine and placebo. Subject participation will last an estimated 10-14 weeks. We anticipate most subjects will participate for 10 weeks, however due to unforeseen circumstances a subject may be unable to keep a scheduled appointment lengthening the overall time of their participation. In order to test our hypotheses, we use the following outcome measures, at time of each evaluation. A. Eye movement assessment: changes in binocular horizontal conjugacy at baseline and following the saccadic fatigue test using 1) abducting/adducting eye ratio for saccadic peak velocity (pulse size ratio); 2) time difference in occurrence of peak acceleration in the adducting vs. the abducting eye (pulse time delay). These measures of conjugacy of horizontal saccades are applied to data collected continuously throughout the fatigue test. B. Symptomatic fatigue assessment using 1) Fatigue Severity Scale (FSS); 2) Modified Fatigue Impact Scale (MFIS); C. Visual function assessment using 1) MNREAD acuity charts for reading acuity and speed; 2) King-Devick test for saccades performance; D. Gait assessment using 1) 25-foot Walk Test; 2) 6-minute Walk Test. E. Visual disability and quality of life assessment using 1) NEI-VFQ-25 and NOS; 2) MS Quality of Life Inventory. Standard statistical measures, such as paired dependent t-test, will be employed to determine significance of our results.

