**Eye Movement Recording (one session only).** Eye movements will be recorded using the EyeLink II system, (SR Research Ltd.). Normal controls will sit in a 110-ft-lb vestibular chair (CNC Engineering), with head restrained, during all the experimental paradigms, and will follow a visual stimulus (a red laser spot) projected onto tangent screen. The EyeLink signal from each eye will be calibrated. We will obtain a baseline monocular and binocular viewing recording of eye movements then will perform the 10-minute saccadic fatigue test as previously described [Matta et al, 2009]. Normal controls will make horizontal saccades in response to 20-degree jumps, at 0.5 Hz across the midline (i.e., 1 saccade per second), of the visual target (laser spot).

The table below summarizes the randomized, placebo-controlled, double-blind, crossover trial design, which will include a period of wash-out of at least two weeks between treatment with dalfampridine and placebo. In the event the washout period lasts longer than 2 weeks or a subject has difficulty keeping one of the study visits and needs to reschedule, subject participation would be greater than 10 weeks (estimated 10-14 weeks of participation).

[figure not shown]

Table. Flow diagram summarizing study design. Following enrollment and randomization subjects will undergo a total of 4 evaluations, each one consisting in: eye movement recording, symptomatic fatigue assessment, visual function assessment, gait assessment, visual disability and quality of life assessment. Renal function panel (serum) will be performed at baseline, to be repeated after 4 weeks and at the end of the trial. See text for details.

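### Must the plan name which of the two eye-movement recordings at Evaluations 2 and 4 enters the drug-versus-placebo comparison?

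*Combined protocol and SAP*

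**What the plan says.** In Section 3, item 13 (Eye Movement Recording), the two on-treatment visits are set up in one sentence: "At evaluations 2 and 4, patients will hold the am dose (dalfampridine or placebo", after which they "will undergo baseline eye movement recording, then will be recorded again 3 hours after taking their dose in the same session". For every evaluation the same item gives the sequence within a recording: "We will obtain a baseline monocular and binocular viewing recording of eye movements then will perform the 10-minute saccadic fatigue test".

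Item 10 lists the visits: "There will be a total of 4 evaluations: at baseline, after washout, and after treatment with both dalfampridine and placebo". It describes assessment as "using available self-administered questionnaires and scales, and eye movement recording, before and after treatment" and defines the eye-movement outcome as "changes in binocular horizontal conjugacy at baseline and following the saccadic fatigue test". It adds that the two conjugacy measures are computed on saccades gathered over the whole length of the fatigue test. The named method is a paired t-test; what forms the pair is not stated. Item 11 does not tie its effect size of 0.5 to either recording. The caption of the flow diagram describes the evaluations as "each one consisting in: eye movement recording, symptomatic fatigue assessment, visual function assessment, gait assessment, visual disability and quality of life assessment", with no split into before and after the dose.

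**The concern.** Two recordings exist at each on-treatment visit and the analysis section treats the visit as a single time point. Three drug-versus-placebo contrasts could be built: the held-dose recording, the 3-hour recording, or the change between them. They estimate different things. The first is what remains after about 4 weeks with the morning dose withheld, the second is the effect shortly after a dose, and the third is the acute effect of one dose on top of the 4 weeks.

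The word *baseline* adds to the unease. In item 10 it names the first evaluation. In item 13 it names the recording before the fatigue test, and also the held-dose recording at Evaluations 2 and 4. A reader could take that last one for an untreated reference, which it is not: item 40 gives twice-daily dosing about 12 hours apart, so the patient is still on treatment.

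The stake is twofold. A contrast chosen after the data are seen would raise the false-positive rate. And if the fatigue change ran from the held-dose recording to a fatigue test after the dose, it would mix two effects that the hypothesis lists separately: "dalfampridine improves visual performance in MS patients with INO and counteracts ocular motor fatigue".

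**Working it through.** **The plan's own figure.** Item 11 gives 27 patients for effect size 0.5, alpha 0.05 and power 0.85. The paired normal formula n = ((z_alpha + z_power)/d)², one-sided, gives ((1.645 + 1.036)/0.5)² = 28.8, so 29, which is close to 27. The exact one-sided t calculation gives 31; the two-sided values are 36 (normal) and 38 (t). Sidedness is not stated, which is a separate matter. Naming a recording does not alter this sum. At the planned 30 patients and d = 0.5, power is 0.848 one-sided or 0.754 two-sided for any single contrast that carries the full effect.

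**Type I error if the contrast is chosen after the fact.** Inputs: 30 patients (item 11), a paired t-test (item 10), alpha 0.05 taken as two-sided (assumed), no true effect. The correlation r between the drug-minus-placebo differences at the two recordings is not in the documents, so it is varied.

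- Two independent candidates: 1 − (1 − 0.05)² = 0.0975.
- Correlated candidates, from two separate simulations (200,000 and 100,000 null trials per setting):

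| r | Either recording | Either recording or their difference |
|---|---|---|
| 0.3 | 0.095 | 0.121 to 0.122 |
| 0.5 | 0.092 | 0.123 to 0.124 |
| 0.7 | 0.083 to 0.084 | 0.122 to 0.123 |
| 0.9 | 0.070 to 0.071 | 0.115 to 0.116 |

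With one contrast fixed in advance, the rate is 0.05 whichever recording it uses. There are two eye-movement measures, and testing both with one fixed contrast each already gives up to 1 − 0.95² = 0.0975 if they are independent. Naming a recording would not remove that part.

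**Does the text support the harmful readings?**

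1. *Fatigue change across the dose.* Item 9 describes ocular motor fatigue as a change seen during a 10-minute recording. Item 10 applies the measures to saccades throughout the test. Item 13 describes one unbroken sequence of rested viewing followed by the test. All three point to a change within a single recording. A start point 3 hours and one dose earlier is the least natural reading.
2. *Held-dose recording as untreated reference.* Item 13 uses *baseline* for the start of a session shortly before it uses the word for the held-dose recording, so the second use can carry the same sense. Item 10 classes Evaluations 2 and 4 as after treatment. No sentence uses the held-dose value as a pre-treatment reference.
3. *Within-session difference as the treatment effect.* Item 10 frames assessment around treatment, and item 13 defines treatment as 4-week periods. No sentence offers the acute change as the treatment effect. On the text, the realistic candidates are the two recordings themselves, so the middle column of the table is the fairer range.

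**Is either matched contrast sound?** The dose is held, the first recording made, the dose taken and the second recording made in the same way under drug and under placebo. Comparing like with like across periods therefore gives a valid test from either recording.

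**The case for a change.** The best argument for a change is that pre-specification exists for exactly this case. Blinding during data collection does not stop someone choosing between two recordings once the code is broken, and naming one would cost a sentence. The choice also matters for power. If the held-dose recording carried only 75%, 50% or 25% of an effect of 0.5 SD (assumed shares, same SD), two-sided power at 30 patients would be 0.51, 0.26 or 0.10, against 0.75 for a recording with the full effect. Nor does the plan say whether the fatigue test is run once or twice at these visits, or when reading, King-Devick and walking tests fall relative to the dose.

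Much of this stands as description. No surviving text names the recording, the label is loose, and the order of the other tests is open. The flow diagram is not shown, and the fatigue test is defined partly by a cited study that cannot be consulted here; neither is likely to settle the drug comparison.

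The argument does not show that the plan gives a wrong answer. The inflation requires selection on the results, and the power loss requires choosing the weaker recording. The lists of tests are not presented as a time order, so their differing order is not a contradiction. Any order kept the same in both periods leaves those comparisons matched too.

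**Conclusion.** The silence is real, but no change to the plan is needed. The plan states no rule that yields a biased estimate or an invalid test. Any single matched recording, fixed before the treatment code is known, closes the gap, and an analyst following items 10 and 13 would ordinarily compare the same recording under drug and placebo and measure fatigue within one recording. Calling the held-dose recording *baseline* is loose wording for the start of the session.

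The size is conditional. If the recording were picked after seeing the results, two-sided type I error per measure would be about 0.07 to 0.095 with the two recordings as candidates, and about 0.12 with their difference added. This assumes 30 complete pairs, correlations of 0.3 to 0.9 and selection of the best result. Without such selection it is 0.05. A reader of the eventual report should check that the same recording was used in both periods and that the choice was made before unblinding.
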